4.1.2. Study Day

If a visit/reporting date is on or after Day 1, then the study day at the visit/reporting date will be calculated as follows:

Day # = (visit/reporting date - Day 1 date + 1).

If the visit/reporting date is before Day 1, then the study day at the visit/reporting date will be calculated as follows:

Day # = (visit/reporting date - Day 1 date).

A study day of -1 indicates 1 day before Day 1.

4.1.3. Baseline Value

Baseline is the last nonmissing measurement obtained before (or on) the day of first application of ruxolitinib cream.

4.1.4. Handling of Missing and Incomplete Data

In general, values for missing data will not be imputed unless methods for handling missing data are specified in this section or relevant sections. The original reported dates collected on the eCRF should be used in all relevant listings. The following rules will be used for handling partial dates for analyses requiring dates.

4.2. Variable Definitions

4.2.1. Body Mass Index

Body mass index will be calculated as follows:

BMI $(kg/m^2) = [weight (kg)] / [height (m)]^2$.

4.2.2. Prior and Concomitant Medication

Prior medication is defined as any nonstudy medication started before the first application of ruxolitinib cream 1.5%.

Concomitant medication is defined as any nonstudy medication that is started accordingly:

- Before the date of first application of ruxolitinib cream 1.5% and is ongoing throughout the study or ends on/after the date of first application of study treatment.
- On/after the date of first application of ruxolitinib cream 1.5% and is ongoing or ends during the course of study treatment.

A prior medication could also be classified as "both prior and concomitant medication," if the end date is on or after the first application of ruxolitinib cream 1.5%. In the listing, it will be indicated whether a medication is prior-only, concomitant-only, or both prior and concomitant.

For the purposes of analysis, all medications will be considered concomitant medications unless the medications can unequivocally be defined as not concomitant.

5. STATISTICAL METHODOLOGY

5.1. General Methodology

Unless otherwise noted, SAS[®] software (SAS Institute Inc, Cary, NC; v9.1 or later) will be used for the generation of all tables, graphs, and statistical analyses. Descriptive summaries for continuous variables will include, but not be limited to, the number of observations, mean, standard deviation, median, minimum, maximum, first quartile, third quartile, and 95% CI. Descriptive summaries for categorical variables will include the number and percentage of participants in each category.

5.2. Treatment Groups

This is an open-label study composed of a 48-week treatment period, including a 12-week treatment run-in. During the 12-week run-in, all participants will apply ruxolitinib 1.5% cream BID. Following these 12 weeks, participants will receive either ruxolitinib 1.5% cream BID alone or ruxolitinib 1.5% cream BID plus NB-UVB phototherapy for 36 weeks. Participant groups were determined based on their T-VASI score at Week 12. Data will be summarized based on the treatments that the participant received.

5.3. Analysis Populations

5.3.1. All-Screened Population

The all-screened population will include all participants who signed the informed consent form.

5.3.2. Full Analysis Set

The FAS will include all participants who applied at least one dose of ruxolitinib cream.

The FAS will be used for the summary of demographics, baseline characteristics, participant disposition, and analyses of all efficacy and safety data.

5.3.3. Pharmacokinetic-Evaluable Population

The PK-evaluable population includes participants who applied at least 1 dose of ruxolitinib cream and provided at least 1 postdose blood sample. The study pharmacokineticist will review data listings of participant administration and sample records to identify participants to be excluded from the analyses.

5.3.4. Pharmacodynamic-Evaluable Population

The PD-evaluable population will include all participants who applied at least 1 dose of ruxolitinib cream and provided at least 1 PD measurement that complies with the instructions in the Protocol. The study research investigator will review data listings of PD data and sample records to identify participants to be excluded from analyses of PD data.

6. BASELINE, EXPOSURE, AND DISPOSITION VARIABLES AND ANALYSES

Appendix A provides a list of planned tables, figures, and listings. Sample data displays are included in a separate document.

6.1. Demographics, Baseline Characteristics, and Disease History

6.1.1. Demographics and Baseline Characteristics

The following demographics will be summarized for the FAS population: age, age group, sex, race, ethnicity, region, weight, height, and BMI.

6.1.2. Baseline Disease Characteristics and Disease History

The following baseline disease characteristics will be summarized for the FAS population and will include, but will not be limited to the following:

- Time since initial diagnosis of vitiligo
- Vitiligo diagnosed in childhood (no/yes [age]: 0-5 years, 6-11 years, 12-17 years)
- Disease status (stable/progressive)
- Skin type (Fitzpatrick scale Type I/II/III/IV/V/VI)
- Other autoimmune disorders
- Prior therapy given for vitiligo (predefined systemic treatments, phototherapy, and surgical procedures)
- History of acne vulgaris (no/yes)
- Currently have acne vulgaris on the face (no/yes)
- Itching associated with the vitiligo lesions (no/yes)
- Vitiligo in genital area (no/yes)
- Baseline F-VASI
- Baseline T-VASI
- Baseline F-BSA involvement (% of the total body)
- Baseline T-BSA involvement (% of the total body)

6.1.3. Prior Medication for Vitiligo

Prior medication information for vitiligo will be used to identify other nonpredefined medication received by participants before enrollment into the study. Prior medication for vitiligo will be summarized by treatment group.

6.1.4. Medical History

For participants in the FAS, medical history will be summarized by treatment group. This summary will include the number and percentage of participants with medical history for each body SOC/PT as documented in the eCRF.

6.2. Disposition of Participants

The number and percentage of participants who were enrolled, who were treated, and who completed the study for each period will be summarized for the ITT population.

6.3. **Protocol Deviations**

Protocol deviations recorded on the eCRF will be summarized and listed.

6.4. Exposure

For participants in the FAS population during the treatment period, exposure will be summarized descriptively for duration of treatment, average daily dose, and total dose.

6.5. Study Drug Compliance

For the participants in the FAS population, overall compliance (%) for the application of ruxolitinib cream during the treatment period will be calculated for all participants as follows:

Compliance (%) of ruxolitinib cream = $100 \times [\text{total number of applied applications}] / [\text{total number of prescribed applications}].$

The total number of intended applications is the number of planned applications minus the number of interrupted applications.

6.6. NB-UVB Machine Compliance

Overall compliance (%) for the NB-UVB machine will be calculated by the number of sessions recorded by the NB-UVB machine.

Compliance (%) of NB-UVB = $100 \times [\text{total number of days using NB-UVB}] / [\text{total number of days intended to use NB-UVB}]$

The total number of days intended to use is the number of days prescribed based on the frequency of 3 days per week. Compliance will be summarized and listed for participants in Group A.

6.7. Prior and Concomitant Medication

Prior medications and concomitant medications will be coded using the WHO Drug Dictionary. The number and percentage of participants in the safety population for each prior and concomitant medication will be summarized by WHO drug class and WHO drug preferred term. Prior and concomitant medications will also be summarized (and listed) by treatment group.

7. EFFICACY

Appendix A provides a list of data displays. Sample data displays are included in a separate document.

7.1. General Considerations

For all continuous variables, the actual value and change and/or percentage from baseline (if available) will be analyzed.

For continuous measurements, summary statistics will include sample size, mean, median, standard deviation, standard error of the mean, minimum, and maximum.

For categorical measurements, summary statistics will include sample size, frequency, and percentages. All by-visit analyses will include the follow-up period, if the data are available.

7.2. Efficacy Measures

7.2.1. Body Surface Area

Total % BSA (includes facial and nonfacial areas) depigmented by vitiligo will be estimated at each visit. Body surface area assessment will be performed by the Palmar Method. Body surface area should be estimated to the nearest 0.1%. The approximate size of the participant's entire palmar surface (ie, the palm plus 5 digits) should be considered as 1% BSA; the approximate size of the participant's thumb should be considered as 0.1% BSA.

7.2.2. Vitiligo Area Scoring Index

Areas affected by depigmentation due to vitiligo will be assessed using the VASI. It is based on a composite estimate of the overall area of vitiligo patches at baseline and the degree of macular repigmentation within these patches over time.

Facial VASI is measured by percentage of vitiligo involvement (% BSA) and the degree of depigmentation. The percentage of BSA (hand unit) vitiligo involvement is estimated by the investigator using the Palmar Method. The hand unit is based on participant's hand size. The investigator uses his/her hand to mimic the participant's hand size to evaluate percentage BSA vitiligo involvement. The degree of depigmentation for each vitiligo involvement site is determined and estimated to the nearest of the following percentages: 0%, 10%, 25%, 50%, 75%, 90%, or 100%. At 100% depigmentation, no pigment is present; at 90%, specks of pigment are present; at 75%, the depigmented area exceeds the pigmented area; at 50%, the depigmented and pigmented area are equal; at 25%, the pigmented area exceeds the depigmented area; and at 10%, only specks of depigmentation are present. The F-VASI is then derived by multiplying the values assessed for the vitiligo involvement by the percentage of affected skin for each site on the face, summing the values of all sites together (possible range, 0-3).

The area "Face" is defined as including the area on the forehead to the original hairline, on the cheek to the jawline vertically to the jawline and laterally from the corner of the mouth to the tragus. The area "Face" will not include surface area of the lips, scalp, ears, or neck, but will include the nose and eyelids.

Total body VASI is calculated using a formula that includes contributions from all body regions (possible range, 0-100).

The body is divided into the following 6 separate and mutually exclusive sites: 1) head/neck, 2) hands, 3) upper extremities (excluding hands), 4) trunk, 5) lower extremities (excluding feet), and 6) feet. The percentage of vitiligo involvement is estimated in hand units (% BSA) by the same investigator during the entire course of the study. Hand unit is based on participant's hand size. The investigator uses their hand to mimic the participant's hand size to evaluate % BSA vitiligo involvement. The degree of depigmentation for each body site is determined and estimated to the nearest of the following percentages: 0%, 10%, 25%, 50%, 75%, 90%, or 100%. The T-VASI is then derived by multiplying the values assessed for the vitiligo involvement by the percentage of affected skin for each body site, summing the values of all body sites together (Hamzavi et al 2004).

CONFIDENTIAL

7.3. Efficacy Analysis

7.3.1. Primary Efficacy Analysis

The primary efficacy endpoint is the change from baseline in T-VASI at Week 48. For the primary endpoint, summary statistics will include sample size, mean, median, standard deviation, minimum, maximum, and the 95% CI.

7.3.2. Secondary and Efficacy Analysis

7.3.2.1. Continuous Efficacy Endpoints

By-visit summary statistics for the following continuous measurements, including actual measurement, change from baseline, and percentage change from baseline, will be presented:

• F-VASI/T-VASI

Summary statistics, including sample size, mean, median, standard deviation, minimum, maximum, first quartile, third quartile, and 95% CI, will be presented by visit. In addition, line graphs and mean and standard error plots will be provided.

7.3.2.2. Categorical Efficacy Endpoints

For the following categorical parameters, summary statistics will include sample size, frequency, percentages and standard error of percentage, and the 95% CI at each visit. In addition, box plots will be provided.

- Proportion of participants achieving F-VASI50/75/90
- Proportion of participants achieving T-VASI25/50/75/90

8. PHARMACOKINETICSAND PHARMACODYNAMICS

8.1. Pharmacokinetic Analyses

Trough plasma ruxolitinib concentrations at applicable study visits will be summarized using descriptive statistics by treatment group.

8.3. Pharmacokinetic/Pharmacodynamic Analyses

Pharmacokinetic analyses will be performed using the PK-evaluable population.

9. SAFETY AND TOLERABILITY

Appendix A provides a list of data displays. Sample data displays are included in a separate document.

9.1. General Considerations

The analyses in this section will be provided for the safety population.

Summary tables may be replaced with listings when appropriate. For instance, an AE frequency table may be replaced with a listing if it only contains a few unique PTs reported on relatively few participants.

9.2. Adverse Events

9.2.1. Adverse Event Definitions

A TEAE is any AE either reported for the first time or worsening of a pre-existing event after first application of study drug and within 30 days of the last application of study drug. For participants who have NB-UVB phototherapy added, the first application date is period-specific, and the end date is 30 days after the last application date in this period, or the day before the first application date in the next period, whichever comes first. Analysis of AEs (as discussed below) will be limited to TEAEs, but data listings will include all AEs regardless of their timing in relation to study drug application.

Adverse events will be tabulated by MedDRA PT and SOC. Severity of AEs will be graded using the NCI CTCAE v5. The CTCAE reporting guidelines and grading details are available on the Cancer Therapy Evaluation Program website.

The subset of AEs considered by the investigator to be related to study drug will be considered to be treatment-related AEs. If the investigator does not specify the relationship of the AE to study drug, the AE will be considered to be treatment-related. The incidence of AEs and treatment-related AEs will be tabulated. Serious AEs will also be tabulated.

Any missing onset date, causality, or severity must be queried for resolution. Unresolved missing causality and severity will be handled according to the following rules:

- An unresolved missing causality will be considered treatment-related.
- An unresolved missing severity will be identified as an unknown severity.

For purposes of analysis, all AEs will be considered TEAEs unless the AE can unequivocally be defined as not treatment-emergent.

Application site reactions are AEs that occur at the site of drug application. A summary of ASRs will be provided.

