#### 4. STUDY DESIGN

### 4.1. Overall Design

This is an open-label study in which participants will apply ruxolitinib 1.5% cream BID to all depigmented areas up to 10% BSA for up to 48 weeks. Participants should continue to treat depigmented areas identified for treatment at baseline regardless of whether the area begins to improve or fully repigment.

On Day 1, all participants will apply ruxolitinib 1.5% cream BID as monotherapy (see Figure 1). At Week 12, participants will apply ruxolitinib 1.5% cream alone or in combination with NB-UVB based on improvement in T-VASI score. Participants who have < T-VASI25 will have NB-UVB phototherapy added to their ruxolitinib 1.5% cream BID regimen (Group A). NB-UVB will be given 3 times per week through Week 48 (36 weeks). Participants who have  $\geq$  T-VASI25 at Week 12 will continue on ruxolitinib 1.5% cream BID alone (Group B). For participants who receive combination therapy, NB-UVB machines will be supplied by the sponsor for at home use during the study.

At any time during the study, if vitiligo areas become significantly more extensive than from the previous visit, the participant should contact the study site to discuss with the investigator whether additional evaluation at the clinic is required. Participants who have expansion of areas of vitiligo identified at baseline or new areas of vitiligo during the course of the treatment period should not treat the additional areas of vitiligo with ruxolitinib cream.

Participants who permanently discontinue NB-UVB will be allowed to remain in the study and continue to apply ruxolitinib 1.5% cream BID alone. Participants who permanently discontinue ruxolitinib 1.5% cream BID will be allowed to remain in the study and continue NB-UVB phototherapy alone.

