4. DATA HANDLING DEFINITIONS AND CONVENTIONS

4.1. Scheduled Study Evaluations and Study Periods

4.1.1. Day 1

Day 1 is the date that the first application of ruxolitinib cream is administered to participants in the specific period.

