9.2.2. Adverse Event Summaries

An overall summary of AEs by treatment group will include the following:

- Number (%) of participants reporting any TEAEs
- Number (%) of participants reporting any serious TEAEs
- Number (%) of participants reporting any Grade 3 or higher TEAEs
- Number (%) of participants reporting any treatment-related TEAEs
- Number (%) of participants who temporarily interrupted study drug because of TEAEs
- Number (%) of participants who permanently discontinued study drug because of TEAEs
- Number (%) of participants who had a fatal TEAE

The following summaries will be produced by MedDRA term (if 5 or fewer participants appear in a table, a listing may be appropriate):

- Summary of TEAEs by SOC, PT, and maximum severity
- Summary of TEAEs by SOC and PT
- Summary of TEAEs by PT in decreasing order of frequency
- Summary of Grade 3 or higher AEs by SOC and PT
- Summary of Grade 3 or higher AEs by PT in decreasing order of frequency
- Summary of serious TEAEs by SOC and PT
- Summary of serious TEAEs by PT in decreasing order of frequency
- Summary of ASRs by SOC and PT
- Summary of ASRs by PT in decreasing order of frequency
- Summary of treatment-related TEAEs by SOC and PT
- Summary of treatment-related TEAEs by PT in decreasing order of frequency
- Summary of Grade 3 or higher treatment-related TEAEs by SOC and PT

CONFIDENTIAL

- Summary of treatment-related serious TEAEs by SOC and PT
- Summary of TEAEs with a fatal outcome by SOC and PT
- Summary of TEAEs leading to dose interruption of study drug by SOC and PT
- Summary of TEAEs leading to discontinuation of study drug by SOC and PT

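### SAP 9.2.1 splits the TEAE window by period only for participants given NB-UVB, so AE percentages by treatment group rest on unequal observation times, in a direction the SAP leaves open

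*SAP*

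**What the plan says.** SAP 9.2.1 first gives a general rule: an AE is treatment-emergent if it is new or worsens "after first application of study drug and within 30 days of the last application of study drug". It then adds a rule for part of the study population: "For participants who have NB-UVB phototherapy added, the first application date is period-specific". For those participants each window ends 30 days after the last application in the period, "or the day before the first application date in the next period, whichever comes first". The section gives Group B no corresponding split.

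SAP 4.1.1 does not match this. It defines Day 1 by the first cream application "administered to participants in the specific period", without limiting that to participants who receive NB-UVB.

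On tabulation, SAP 9.2.2 states: "An overall summary of AEs by treatment group will include the following". The entries are numbers and percentages of participants. SAP 5.2 adds: "Data will be summarized based on the treatments that the participant received". Neither section defines the columns or places Group A's run-in events. No exposure-adjusted rate appears in SAP 9.2 or among the AE tables of Appendix A, and no AE table title there names a period.

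Protocol Table 15 (Section 10.4.2) has one TEAE definition with no split by period. SAP 11.1 nevertheless records no change to protocol-defined analyses.

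**The concern.** A percentage of participants with at least one event rises with the time they are watched. If one column covers a longer window than another, the percentages differ even when the underlying risk is the same. Here the rule that sets the window differs by group, and the column definition that would show its effect is missing.

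Safety and tolerability of the combination is the first-listed secondary objective in both documents, and the by-group AE table is where readers will look for it. They will compare the columns whether or not a test is planned. Two programmers following the SAP text faithfully could produce tables that point in opposite directions.

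**Working it through.** **Inputs**
- Treatment period and run-in (SAP 5.2): "This is an open-label study composed of a 48-week treatment period, including a 12-week treatment run-in".
- Combination period: 36 weeks (Protocol 4.1).
- Follow-up: 30 days = 30/7 = 4.3 weeks (SAP 9.2.1).
- Participants: about 50 (SAP 3.3).
- Expected Group B share: 21.2%, the proportion on 1.5% BID with T-VASI25 at Week 12 in the sponsor's earlier Phase 2 study (Protocol 2.4). This gives 50 × 0.212 = 10.6 in Group B and 39.4 in Group A.
- Illustrative 24-week risks from that study, pooled over active arms (Protocol 2.3): any TEAE 67.2%, acne 12.0%.

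**Plan's own figure.** 48 − 12 = 36 weeks, as stated.

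**Windows**
- Group A run-in: 12 weeks.
- Group A combination: 36 + 4.3 = 40.3 weeks.
- Group B, unsplit: 48 + 4.3 = 52.3 weeks. The ratio 40.3/52.3 is 0.77.

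**Risk model (assumed).** Constant hazard, the same in both groups, with full follow-up: risk over t weeks = 1 − exp(−h·t), where h = −ln(1 − p)/24.
- Any TEAE: h = −ln(0.328)/24 = 0.0464 per week. Risks: 42.7% at 12 weeks, 84.6% at 40.3, 91.2% at 52.3.
- Acne: h = −ln(0.88)/24 = 0.0053 per week. Risks: 6.2%, 19.3% and 24.3%.

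**Three readings of the columns**

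1. *Combination period against Group B's whole study.* Windows are 40.3 and 52.3 weeks.
2. *Columns by treatment received, with Group A's run-in under cream alone.* The mean cream-alone window is (39.4 × 12 + 10.6 × 52.3)/50 = 20.5 weeks, against 40.3. Any TEAE under cream alone is (39.4 × 42.7% + 10.6 × 91.2%)/50 = 53.0%. The same sum for acne gives 10.0%.
3. *Both Group A periods added together.* 12 + 40.3 = 52.3 weeks, against 52.3.

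| Reading | Any TEAE: combination vs cream alone | Acne: combination vs cream alone | Apparent effect at equal risk |
|---|---|---|---|
| 1 | 84.6% vs 91.2% (−6.6 points) | 19.3% vs 24.3% (−5.0) | Combination looks safer |
| 2 | 84.6% vs 53.0% (+31.6 points) | 19.3% vs 10.0% (+9.3) | Combination looks less safe |
| 3 | 91.2% vs 91.2% | 24.3% vs 24.3% | None from window length |

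Under reading 2 the mean windows become equal only if (40.3 − 12)/(52.3 − 12) = 70% of participants are in Group B, far above the 21.2% expected.

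**Sensitivity.** Let the hazard in the first 12 weeks be k times the later hazard, keeping the 24-week total.

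| k | Combination, any TEAE | Group B whole study (reading 1) | Cream alone pooled (reading 2) |
|---|---|---|---|
| 2 | 71.3% | 86.3% | 59.6% |
| 3 | 60.8% | 83.0% | 62.2% |

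Early clustering widens the gap in reading 1 to 15 to 22 points. In reading 2 it narrows the gap and at k = 3 nearly removes it.

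**After the fix.** Both post-Week-12 windows are 40.3 weeks. At equal constant risk both groups show 84.6% with any TEAE and 19.3% with acne. The run-in is one common 12-week window (42.7% and 6.2%).

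**The case against.** A reader might infer that the rule makes the combination look safer, because its window is the shorter one. That is reading 1 only. The SAP does not say that its AE tables make this comparison, and summarizing by treatments received equally permits reading 2, where the sign reverses at constant risk. The documents do not support a fixed direction.

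The defence has further points:

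- *The split may be meant for everyone.* SAP 4.1.1 is worded generally, SAP 5.2 describes a run-in followed by 36 weeks for both groups, and SAP 6.2 reports disposition by period. That is possible, but it then conflicts with 9.2.1, which names only participants with NB-UVB added.
- *The table shells may settle the columns.* They are in a separate document. This stands as a limit on what can be concluded. Still, the SAP text should carry the rule. The one group-specific AE title in Appendix A (Table 3.2.8.3, Cohort A) does not help, since its note describes TEAEs related to either treatment, not a period.
- *An AE that begins in the run-in and does not worsen is properly not emergent on the combination.* This is correct. It remains a TEAE of Group A's first period, and listings include all AEs. The point rests on window length, not on such events.
- *The practical weight is limited.* No between-group test is planned, and the safety objective concerns the combination itself. With about 10.6 participants in Group B, the 6.6-point gap of reading 1 is about 0.7 of a participant, against a binomial standard error of √(0.912 × 0.088/10.6) = 8.7 points. This stands for reading 1. The reading 2 gap is much larger.
- *Reading 3 gives equal windows.* It does, but the two abutting windows then rebuild the general window, so the period rule has essentially no effect, and cream-alone run-in events are credited to the combination group.

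**Conclusion.** The point holds as a defect of specification with a numerical consequence. The TEAE rule is period-specific for one group only, the AE columns are undefined, and crude percentages are planned without person-time. In any reading where the rule has an effect, the observation windows are unequal. At equal constant risk the any-TEAE difference (combination minus cream alone) runs from −6.6 to +31.6 points depending on a choice the SAP does not state.

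These figures show size and direction and do not forecast results. They assume a common hazard and full follow-up, and they use rates pooled over several strengths in an adult study. The 20.5-week mean also assumes that the 21.2% responder share carries over.

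Equal windows would remove the observation-time artefact and nothing more. Group A is formed from those below T-VASI25 at Week 12 and Group B from those at or above it, so the groups are not otherwise comparable, and Group B is small. With no formal comparison planned, this should be corrected but does not threaten the primary analysis.

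**What to change.** 1. In SAP 4.1.1 and 9.2.1, apply the same Week 12 split to all participants, and keep study day anchored to the first-ever cream application.
2. In SAP 9.2.2, define the columns: (i) Day 1 to Week 12, all FAS participants on cream alone; (ii) Week 12 to 30 days after last application, by Group A and Group B. State that Group A's run-in events belong to (i).
3. Add exposure-adjusted rates (events per person-time) to the overall TEAE table. They complement the split and do not replace it, because a rate alone does not correct for events that cluster early in cream use.
4. Record the period-specific TEAE window in SAP 11.1 as a change from the protocol's single definition.

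The cost is SAP wording and one more column set in the AE tables. No new data are needed.
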